This study will be a large, multi-center, randomized prospective trial for TAP block, evaluating postoperative pain, PONV, hospital stay and other surgical outcomes.

Study Population and Design

The study design will be a multi-center, double-blinded, prospective, randomized controlled trial comparing Marcaine (bupivacaine) with normal saline in a transversus abdominis plain block in adult patients who have undergone elective laparoscopic colorectal surgery.

The purpose of this study will be to prove the effectiveness of local anesthetic given via a TAP block in improving postoperative pain, postoperative opioid use, PONV and surgical outcomes such as hospital length of stay in laparoscopic colorectal surgery when compared to controls.

The study will randomize adult patients with benign and malignant conditions of the colon and rectum that require elective laparoscopic right, total, and left colectomy into two groups. Subjects meeting the inclusion criteria will be informed about the trial, and requested to participate after the informed consent process.

Recruitment

The patients will be recruited from the Departments of Colorectal Surgery of University Hospitals of Cleveland OH as well as approximately 3 to 6 other institutions across the United States. The patient population in this study will be candidates of either sex, over 18 who have benign or malignant colonic or rectal disease in which resection is required via a laparoscopic approach. The patients will be asked to participate in the study after evaluation by either the PI or the co-investigators and candidacy for either procedure has been established. The investigator will discuss the study with the patient and the study coordinator will participate in patient recruitment. Patients will be recruited until at least 75 participants are enrolled from all institutions, with up to 75 patients enrolled from UHCMC if other institutions do not participate.

Inclusion criteria:

1. Subjects who have benign or malignant colonic or rectal disease that are being scheduled for laparoscopic colorectal resection.
2. Subjects who are 18 years of age and older
3. Subjects of either sex
4. Subjects who are willing and able to adhere to protocol requirements, agree to participate in the study program and provide written and informed consent.

Exclusion criteria:

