1. Subjects who undergo conversion to the open approach will be excluded from the analysis, as the block will be given at the end of the procedure and is being evaluated for laparoscopic cases.
2. Subjects who are pregnant.

3. Subjects with a medical condition that may interfere with the use of the study medication Bupivacaine.
4. Subjects who have another condition or general disability or infirmity that in the opinion of the investigator precludes further participation in the study.

Study Procedures

Informed consent will be obtained at the time of enrollment into the study. Enrollment will take place during the preoperative visit with the surgeon in the out patient area or in the pre-surgical area on the day of surgery. The patient will undergo routine preoperative assessment, including: surgical informed consent, collection of demographic information, medical/surgical history, physical exam, and routine laboratory testing. All patients will undergo perioperative care using a standardized enhanced recovery pathway, outlined in the enhanced recovery pathway perioperative guidelines for complete care.

Randomization

Randomization will take place in the operating room. A numbered, sealed envelope, corresponding to the patients' assigned study number, will be opened, and the study nurse will provide Marcaine (bupivacaine) or placebo for the OR nurse to prepare. Patient and surgeon will not know which group the patient is randomized to.

Intraoperative

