Using standard surgical procedures, the surgeon will proceed with the planned laparoscopic surgery. All procedures will be done by straight laparoscopic technique according to standard of care. At the completion of the procedure, and under laparoscopic control, patients will have a TAP block placed by the attending surgeon. The clinical research nurse involved in the research will prep the solution to be injected and the surgeon will be blinded as to whether the patient will be receiving normal saline or Marcaine in the TAP blocks. The block will be administered between the costal margin and iliac crest in the anterior axillary line. A Braun Stimuplex A insulated needle (80 mm 21 gauge) with 0.5 mL/kg solution (max of 30 ml) is passed through the skin, and then continued until two distinct "pops" are felt, which indicates the needle piercing each of the two fascial layers. The needle is then deemed to be in the inter-muscular plane between internal oblique and transversus abdominis muscles respectively, to target the spinal nerves in this plane. The laparoscope will be visualizing for the needle tip to ensure that it does not penetrate the peritoneum or inject pre-peritoneally. The local anesthetic is infiltrated in two separate injections into the same plane on each side. If a sub-peritoneal bleb is seen to be raised by the laparoscope, then the needle will be withdrawn slightly. Two thirds of the solution is injected, and the needle is withdrawn 5 mm and the remaining solution is injected. If injecting in the correct plane, then a smooth raised area of fluid, covered by transversus will be seen via the laparoscope. This procedure is repeated on the patients other side, to complete a bilateral block. Refer to the attached TAP block Procedure.doc file for a visual aid to the TAP block procedure. Depending on their randomization, patients will receive one of the following solutions:

Group A: Represents the control group and will receive 0.5 ml/kg of 0.9% normal saline for a maximum of 30 ml.

Group B: Represents the experimental group and will receive 0.5 ml/kg of 0.25% Marcaine (bupivacaine) for a maximum of 30 ml.

Enhanced Recovery Pathway

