All patients will be managed via standardized accelerated postoperative recovery guidelines which are currently in use by the division of colorectal surgery at UHCMC. This includes early overnight patient-controlled analgesia pump, oral analgesia and diet on the first postoperative day, early postoperative ambulation, and defined discharge criteria. The complete guidelines can be viewed at our Guidelines.doc file included.

All Study Patients

The medical/surgical information below will be collected as part of this research study and is all information already available as part of the patients medical chart.

- Patient Demographics (age, gender, BMI, ASA score)
- name of surgeon
- name of procedure
- Estimated blood loss
- Opiate use in PACU (morphine equivalents)
- Time spent in PACU
- daily use of analgesics (PCA and oral) in morphine equivalents
- daily Pain scores while in hospital (maximum and average)
- daily post-operative nausea/vomiting scores
- daily use of antiemetics
- opiate use at discharge, and whether opioids are used at home
- Length of stay in hospital
- day of return of bowel function (flatus and stool)
- Post operative complications, including ileus (defined as reduction in diet and placement of a nasogastric tube)
- 30 day readmission rates

Study Completion

Completion of participation in the study will be 30 days after their date of surgery. Any readmission up to 30 days post-operatively to the hospital as a direct result of their surgery will be followed. The patients will follow-up with the surgeon in the office in approximately 6 weeks which is considered standard of care for all patients undergoing colorectal surgery and is not considered part of the research study.

Patient Withdrawal

Patients can withdraw from the study at any time. Any subject who wishes to withdraw from this study on his/her own accord and for whatever reason is entitled to do so without obligation and prejudice to further treatment. In addition, the investigator may decide for reasons of medical or surgical prudence to withdraw a subject. In either event, the investigator will clearly document the date and reason for the subject's withdrawal from this investigation in the medical chart.

Risks/discomforts

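### Preoperative and intraoperative opioid exposure is not clearly recorded or adjusted for, which costs precision and leaves chance imbalance unchecked in a trial of about 75 patients

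*Combined protocol and SAP*

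**What the plan says.** Study Population and Design sets the aim as "improving postoperative pain, postoperative opioid use, PONV and surgical outcomes such as hospital length of stay", so opioid use and pain are outcomes of direct interest.

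No inclusion or exclusion criterion names opioids. The drug-related exclusion is "Subjects with a medical condition that may interfere with the use of the study medication Bupivacaine". The discretionary one is "Subjects who have another condition or general disability or infirmity that in the opinion of the investigator precludes further participation in the study", which could catch some habitual users but is not directed at them.

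Under All Study Patients, the patient baseline item is "Patient Demographics (age, gender, BMI, ASA score". The opioid amounts start with "Opiate use in PACU (morphine equivalents" and continue with "daily use of analgesics (PCA and oral) in morphine equivalents". Home use appears only in "opiate use at discharge, and whether opioids are used at home". Preoperative pain and intraoperative opioid are not listed.

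The Intraoperative section times the block: "At the completion of the procedure, and under laparoscopic control, patients will have a TAP block placed by the attending surgeon". Most intraoperative opioid therefore precedes it.

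Data analysis/statistics names t-tests, Mann-Whitney tests, repeated measures ANOVA or its rank version, and tests for categorical data. It names no covariate or stratification factor, and its comparison of demographic data does not mention opioid use. Recruitment sets a minimum of 75 participants in total.

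**The concern.** A habitual opioid user is likely to need more opioid after surgery in either arm, whatever the block does. Opioid given during surgery can also carry over into recovery-room opioid use, time in recovery and nausea. Both are sources of outcome variation that exist before the block can act.

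Two things are at stake with about 37 patients per arm. First, this variation stays in the error term when a covariate could remove part of it. Second, the arms may differ by chance in the number of habitual users, and the plan includes no step that would show this or allow for it. The home-use item does not settle the matter. It can be read as habitual use or as use after discharge, and on either reading it carries no dose.

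**Working it through.** **Starting point.** The documents give no power, effect size or SD behind the figure of 75, so it cannot be reproduced. I assume 37 and 38 patients per arm and a two-sided 0.05 level; the plan does not state sidedness. The standard error factor is √(1/37 + 1/38) = 0.231, so the difference detectable with 80% power is (1.96 + 0.84) × 0.231 ≈ 0.65 SD.

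**Is the unadjusted comparison biased?** A simulation of 20,000 trials per setting used an unrecorded binary opioid factor (prevalence 10% to 30%, effect 1 to 1.5 SD) plus a continuous prognostic factor. Mean bias was -0.0004 to 0.002 SD (Monte Carlo error about 0.002) and the type I error was 4.7% to 5.0%. Randomization does its work.

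**Precision, route 1: a mixture of users and non-users.** All inputs are assumptions. Opioid-naive patients use 30 mg (SD 20). A fraction f are habitual users with mean m and SD s.

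- Within-group variance = (1 − f) × 20² + f × s²
- Between-group variance = f(1 − f)(m − 30)²
- Gain from adjustment = total variance / within-group variance

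| Inputs | Within | Between | Total | Total SD | Gain |
|---|---|---|---|---|---|
| f = 0.10, m = 60, s = 30 | 450 | 81 | 531 | 23.0 mg | 531/450 = 1.18 |
| f = 0.15, m = 75, s = 40 | 580 | 258 | 838 | 29.0 mg | 838/580 = 1.45 |

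Adjustment is then worth about 18% to 45% more patients.

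**Precision, route 2: an assumed correlation ρ between covariate and outcome.** Effective N = 75 / (1 − ρ²). Power is for a true difference of 0.5 SD; unadjusted it is 58%.

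| ρ | Effective N | Power |
|---|---|---|
| 0.2 | 78 | 60% |
| 0.3 | 82 | 62% |
| 0.4 | 89 | 66% |
| 0.5 | 100 | 71% |

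The routes agree where they overlap. Route 1 implies ρ = √(81/531) = 0.39 to √(258/838) = 0.55, so its upper case lies slightly beyond the range of route 2.

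**Chance imbalance.** With 8 habitual users among 75 (hypergeometric, 37 in one arm), a split of 6 to 2 or worse has probability 0.26, and 7 to 1 or worse 0.06.

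A 6 to 2 split shifts the arm difference by (6/37 − 2/38) × (m − 30) = 0.1095 × 30 = 3.3 mg, or 0.1095 × 45 = 4.9 mg. The standard error of the difference is 23.0 × 0.231 = 5.3 mg, or 29.0 × 0.231 = 6.7 mg. The shift is therefore about 0.6 to 0.7 of a standard error.

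Simulated under no block effect, with normal outcomes and the split held fixed, the false-positive rates are:

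| Split | t-test | Mann-Whitney |
|---|---|---|
| 6 to 2 | 7% to 8% | 6% to 7% |
| 7 to 1 | 13% to 17% | 10% to 11% |

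The common imbalance has a small effect, and the one with a larger effect is uncommon.

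**The case against.** The strongest answer is that the trial is randomized by sealed envelope with patient and surgeon blinded, so prior opioid use is balanced in expectation and the test keeps its error rate. That stands. A reader might infer that the block's effect is confounded with tolerance or with opioid carried over from surgery; the documents do not support this. One narrower route to bias cannot be excluded. The envelope is opened in the operating room at an unstated moment, and the anesthesia provider is not named as blinded. However, nothing shows that this person learns the arm, and the trial is described as double-blinded.

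A reader might also infer that an imbalance could never be seen or corrected. That goes too far. A medical history is taken before surgery and an anesthesia record should exist, so the items could probably be abstracted later. What would be lost is prespecification: an adjustment chosen after the data are known is less convincing.

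Three further objections have weight. Admitting habitual users is a legitimate pragmatic choice. The planned rank methods dampen a tail of high consumers, so adjustment would probably gain less there. The enhanced recovery guideline is a separate file not available here, and it may limit variation in intraoperative opioid. It could not remove differences in prior tolerance, and it would not make the dose a study data item.

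**Conclusion.** The point holds as one of efficiency and transparency, at the level of something to consider. Opioid use before the block is not an eligibility factor, is recorded at best ambiguously, and plays no part in the analysis of outcomes that it probably predicts.

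The likely gain from adjustment runs from slight (effective N of 78) to useful (effective N of 100, or 45% more patients in the less favorable mixture). Every prevalence, mean, SD and correlation behind these figures is assumed, because the documents give none. The validity of the randomized comparison is not in question.

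**What to change.** In All Study Patients:

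- Replace the home-use item with two: regular preoperative opioid use (yes/no and daily morphine equivalents) and opioid use after discharge, each with a stated time frame.
- Add a preoperative pain score.
- Add intraoperative opioid up to the time of the block, in morphine equivalents, from the anesthesia record.

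In Data analysis/statistics:

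- Prespecify preoperative opioid use as a covariate for the opioid and pain outcomes, and baseline pain as a further covariate for pain scores.
- Report preoperative use and intraoperative opioid by arm.
- Adjust for intraoperative opioid only if it is given before allocation or by someone unaware of the arm. Otherwise it may itself reflect allocation.

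The cost is a few more chart-abstraction fields and a sentence or two in the analysis section. It needs no extra patients, visits or procedures, and no change to eligibility or care.

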The potential risks of this study are those caused by the injection itself and those caused by the medication bupivacaine. Risks of the TAP block injection itself include infection (at injection site and peritoneal), bleeding, transient nerve injury. The risks of the use of bupivacaine include intravascular injection which may cause neurological or cardiovascular complications (confusion, seizure, hypotension, and cardiovascular collapse), local anesthetic toxicity and allergic reaction. Risks of intraperitoneal injection or organ injury will be minimized by laparoscopically-assisted visualization of the needle. Risks of intravascular injection of bupivacaine will be minimized by withdrawal of the syringe to ensure it is not site intravascular prior to injecting. The full details of the risks associated with surgical procedure are explained in the surgical consent form and will be reviewed and discussed with the patient.

Benefits

Because of the nature of this research, there may or may not be any benefits. The study may benefit future patients based on our findings. It is possible that the patients randomized to Group B (Marcaine group) may benefit from decreased length of stay, decreased post-operative nausea/vomiting, less post-operative pain and earlier recovery of gastrointestinal function.

Financial Compensation and Costs

There are no extra costs for the patient associated with the research. Since the surgical procedure is standard of care, any costs related to the surgery will be the responsibility of the patient and his/her insurance company.

Alternative(s) to participation

Patients may also choose not to participate in this study without affecting their surgical treatment. They will receive post-operative analgesia for pain control according to standard of care and the colorectal surgery enhanced recovery pathway guidelines sheet, which may include a TAP block as per the individual surgeon's practice and discussion with the patient. The only other alternative to participation in the study is not to participate.

Plan for obtaining informed consent

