Subject charts and clinical records will be requested and reviewed so that protocol adherence and source documentation can be verified. Information collected from the medical file will be entered into a study spreadsheet to collect data on each subject. The data collection spreadsheet will be kept password protected on Shared Drive in the Department of Surgery in which the principal investigator and the study coordinator have access. Initials will only be used along with surgery date. A separate spreadsheet will be kept of the subject's date of surgery and patient number will be kept on the study coordinator's hard drive in which only she has the password. All data collection forms will be kept under lock and key in the Department of Surgery. Only members of the research team will have access to the documents. The information will only be disclosed with the subject's permission or as required by law. Upon publication, no subjects will be identified and all information will be reported conclusively. There is a possibility that the University Hospitals of Cleveland Institutional Review Board, Food and Drug Administration and possibly foreign regulatory agencies may review the study records.

Data analysis/statistics

Routine statistical analyses will be utilized for parametric and non-parametric datasets, as appropriate. Demographic data will be analyzed using students t-test or Fishers exact test as appropriate. Repeated measurements (pain, nausea scores) will be analyzed by repeated measures ANOVA or ANOVA on ranks. Further paired comparisons at each time interval will be analyzed using the t-test or Mann-Whitney U-test as appropriate. Categorical data will be analyzed using χ^2 analysis or Fishers exact test where applicable. Normally distributed data will be presented as means \pm SD of the mean, non-normally distributed data will be presented as medians \pm quartiles and categorical data will be presented as raw data and frequencies. A P value of > 0.05 will be considered statistically significant.

References

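### Pain scores end at discharge, but the planned repeated measures ANOVA and daily tests name no days and have no rule for series that stop early

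*Combined protocol and SAP*

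**What the plan says.** Under Data analysis/statistics, the combined protocol and SAP states: "Repeated measurements (pain, nausea scores) will be analyzed by repeated measures ANOVA or ANOVA on ranks". It then plans a t-test or Mann-Whitney U-test at each time interval. It names no days and does not mention series of unequal length.

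The data list under All Study Patients includes "daily Pain scores while in hospital (maximum and average" and "daily post-operative nausea/vomiting scores". It describes the items as "all information already available as part of the patients medical chart". The in-hospital limit is explicit for pain. For nausea it is an inference from the chart source. What is followed beyond discharge is opioid use at home and readmission to 30 days, not pain.

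The Enhanced Recovery Pathway section describes "early overnight patient-controlled analgesia pump, oral analgesia and diet on the first postoperative day", then "early postoperative ambulation, and defined discharge criteria". The criteria themselves are not printed: "The complete guidelines can be viewed at our Guidelines.doc file included".

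Study Population and Design lists hospital length of stay among the outcomes that the block should improve. The Benefits section says patients given bupivacaine "may benefit from decreased length of stay, decreased post-operative nausea/vomiting, less post-operative pain".

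**The concern.** Being in hospital on a given day is a post-randomisation event, and the block may change it. From the first discharge onward, a daily test compares whoever remains in each arm, not the randomised groups. A classical repeated measures ANOVA needs every day present for every patient. It therefore excludes anyone discharged before the last day analysed, or someone has to choose a shorter window later, possibly with the data in view.

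Two consequences follow:

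- If discharge is unrelated to pain, there is no bias, but patients and power are lost.
- If discharge depends on pain, the estimated difference can be biased in either direction.

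Dependence is plausible when discharge follows set criteria, but it cannot be checked because the full guidelines are in a separate file.

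A smaller point is that the rank-based alternative is not identified. In context it most likely means repeated measures ANOVA on ranked scores, which keeps the patient as the unit.

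**Working it through.** The plan gives no effect size, SD, power or discharge distribution, so it has no figure to reproduce. The only numerical inputs from the documents are the total of 75 (Recruitment) and the 0.05 level (Data analysis/statistics). Everything else below is assumed, including two-sided testing. POD means postoperative day.

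**1. Loss of power in a single daily test, discharge unrelated to pain.** Power ≈ Φ(d·√(n/2) − 1.96), with n per arm and an assumed difference d = 0.65 SD.

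| Discharged | n per arm | d·√(n/2) | Power |
|---|---|---|---|
| 0% | 37.5 | 2.81 | 80% |
| 20% | 30 | 2.52 | 71% |
| 40% | 22.5 | 2.18 | 59% |
| 60% | 15 | 1.78 | 43% |
| 80% | 7.5 | 1.26 | 24% |

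**2. Simulation inputs.**
- Arms of 38 and 37, with normal scores.
- Control mean 3, 4, 5, 6 or 7, either flat or falling 0.5 per day: 10 settings for each discharge rule.
- Effect -1.0 on every day; between-patient SD 1.4 and residual SD 1.4.
- Everyone observed on POD0 and POD1. From the end of POD1, the daily discharge chance depends on that day's score (at most 3.5 / above 3.5): none 40%/40%, weak 50%/25%, strong 75%/10%.
- The complete-case group test is a t-test on the patient mean over the days analysed. The mixed model has a random patient intercept and separate arm-by-day means.

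**3. Hand check of the no-link case.** Patients still present on POD3: 75 × 0.6 × 0.6 = 27. The SD of a four-day mean is √(1.96 + 1.96/4) = 1.565. The standard error is 1.565 × √(4/27) = 0.602, so the effect is 1/0.602 = 1.66 standard errors. Power ≈ Φ(1.66 − 1.96) = 38%, or 36% from the t distribution; the simulation gave 35-37%. For POD0-1 with all 75, the SD is √(1.96 + 1.96/2) = 1.715 and the standard error 1.715 × √(4/75) = 0.396. The ratio is 2.53 and power about 71%; the simulation gave 68-72%.

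**4. Simulated results, ANOVA through POD3.**

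| Link | Complete-case estimate | Kept of 75 | Complete-case power | Mixed-model power |
|---|---|---|---|---|
| None | -0.99 to -1.02 | 27 | 35-37% | 70-71% |
| Weak | -0.89 to -0.95 in 7 settings, -1.03 to -1.10 in 3 | 23-40 | 33-47% | 68-75% |
| Strong | -0.69 to -0.88 in 9 settings, -1.12 in 1 | 12-55 | 18-56% | 57-76% |

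No-link power was run at mean 5 only. The mixed-model estimate was -0.99 to -1.01 in all 30 settings. In the day-by-day comparison under the strong link (flat mean 5), the in-hospital differences on POD2, 3 and 4 were -0.86, -0.75 and -0.68.

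**5. Dependence on the last day analysed.** With no link and a flat mean of 5, complete-case power through POD2, 3 and 4 is 53%, 35% and 22%, against 71%, 70% and 67% for the mixed model.

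**6. No pain effect, but faster discharge on the block at the same pain score** (control 50%/10%, block 75%/10%; 8 settings). The complete-case difference was +0.11 to +0.68, so the block looks worse. Rejection was 6.4-14.7%, against 4.4-5.6% for the mixed model.

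**7. Second simulation with other inputs** (both SDs 1.5, discharge chance varying smoothly with the previous day's pain, true reduction 1.0). With a link, the POD3 in-hospital reduction was 0.81 to 0.68. About a quarter of patients were complete through POD3, with a mean reduction of 0.79 to 0.60. With no link there was no bias, but POD3 power fell from 52% to 15%.

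**The case against.** The strongest reply is that the plan never commits to an ANOVA through POD3. Cut to POD0-1, the existing method loses nobody under these inputs, and its 68-72% power is level with the mixed model's 70-71%. On that view one sentence naming the days is enough, and changing the method is partly preference. Some software also fits a mixed model under the name repeated measures ANOVA. This much stands: a stated early window avoids the problem for those days, and the mixed model is no more powerful than that window here. But the plan states no such window, the daily tests extend to every interval, and a two-day analysis says nothing about later pain. If a mixed model is meant, a sentence should say so.

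Nearly all inputs are assumed. With no link there is no bias, and under the weak link the bias is at most about 0.1 point. That is correct, but the loss of patients follows from any variation in length of stay.

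The false-positive range in step 6 needs the block to speed discharge at equal pain, although patient and surgeon are blinded. With one discharge rule for both arms and no effect, the complete-case difference was 0.00 to 0.01. That range is a possibility only and should carry little weight.

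Nausea was not simulated, the rank-transformed mixed model was not tested, and the plan names no primary endpoint. The effect on the trial's overall conclusion is therefore unknown.

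**Conclusion.** The concern holds. It follows from the text alone: scores stop at discharge, length of stay is an outcome, and the analysis section names neither days nor a method for series that end early. No other section repairs this. Days before the first discharge are unaffected.

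The size cannot be taken from the documents. Under the assumed inputs, running the classical analysis through POD3 roughly halves power when discharge is unrelated to pain. With a strong link it shrinks a 1-point effect by about 0.1 to 0.3 point in most settings and inflates it in one. Both the direction and the existence of bias depend on a pain-discharge relation that the documents do not show. This is an improvement that should be made; it does not invalidate the trial. Confidence is medium.

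**What to change.** In Data analysis/statistics:

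- Replace repeated measures ANOVA with a linear mixed model on all observed in-hospital days (treatment, day, treatment by day, random patient effect). State which days enter and whether the maximum or the average pain score is analysed.
- If scores are far from normal, fit the same model to rank-transformed scores. This also settles what the rank-based alternative means.
- Add a comparison of each patient's mean score over a fixed early window before discharges begin, by t-test or Mann-Whitney, set before unblinding. POD0-POD1 would fit the overnight pump and first-day oral analgesia, but should be checked against blinded discharge dates. State whether this or the mixed model is the lead analysis.
- Label daily tests after discharges begin as descriptive, and report the number in hospital per arm per day.

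The cost is a few sentences, using scores already on the data list. There are two downsides. Later-day pain becomes supportive only. The mixed model also treats scores after discharge as if they had continued the recorded course, and it removes the bias fully only if discharge depends on recorded scores. When discharge was driven by unrecorded pain under the strong rule, the mixed model gave -0.97 to -1.01 and complete cases -0.76 to -1.10. With no true effect (3 settings) the figures were +0.02 to +0.06 and +0.17 to +0.47. A small bias can therefore remain.

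### Pain and opioid use are to be compared without baseline adjustment, although age, ASA score and procedure are collected on everyone; a short prespecified adjustment would be a cheap gain in precision, but not a free one

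*Combined protocol and SAP*

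**What the plan says.** The Data analysis/statistics section names the outcome methods. For scores over time: "Repeated measurements (pain, nausea scores) will be analyzed by repeated measures ANOVA or ANOVA on ranks". At single time points: "Further paired comparisons at each time interval will be analyzed using the t-test or Mann-Whitney U-test as appropriate"; since the Mann-Whitney test is for independent groups, I read this as pairwise comparison of the two arms. For proportions: "Categorical data will be analyzed using χ^2 analysis or Fishers exact test where applicable". Opioid consumption is not named and falls under the general statement that routine parametric or non-parametric methods will be used. No covariate, stratification factor, ANCOVA, regression or mixed model appears.

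The only stated use of the demographic data is a comparison between arms: "Demographic data will be analyzed using students t-test or Fishers exact test as appropriate".

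The data list under All Study Patients includes "Patient Demographics (age, gender, BMI, ASA score"), "name of surgeon" and "name of procedure". Study Procedures adds a routine preoperative assessment with "collection of demographic information, medical/surgical history, physical exam, and routine laboratory testing". Neither section lists preoperative opioid use or a preoperative pain score.

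The Recruitment section sets enrolment at 75 or more in total, from the lead site and about 3 to 6 others, or from the lead site alone. Study Population and Design puts right, total and left colectomies together, for benign and malignant disease. The Randomization section describes numbered sealed envelopes and no stratification.

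**The concern.** Pain and opioid use can be expected to vary with age, general condition and extent of resection. If they do, an unadjusted test leaves that variation in the error term, and the interval for the treatment difference is wider than it need be. No stratification is described that would balance procedure or site between the arms, and nothing in the analysis accounts for an imbalance that arises by chance.

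This matters more here because the trial is small and has no stated power calculation. The background section itself criticises earlier TAP block studies for being too small. The covariates are already in the data set, so a modest gain would need no extra patients. It would need prespecification, because covariates chosen after the results are seen would carry little weight.

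**Working it through.** **No planned figure to reproduce.** The target of 75 comes with no effect size, SD, power or dropout rate.

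**Inputs from the documents.** Total N = 75 (Recruitment). Significance level 0.05 (Data analysis/statistics; the inequality is printed the wrong way round and is read here as below 0.05).

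**Assumptions.** 1:1 allocation (37 versus 38), two-sided test, true difference of 0.5 SD, one comparison at one time point, and p baseline parameters that explain a share R² of the outcome variance.

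**Step 1, unadjusted.** SE = √(1/37 + 1/38) = 0.231 SD. Noncentrality = 0.5/0.231 = 2.165 on 73 degrees of freedom. Power = **57.0%**. The difference detectable with 80% power is about 0.66 SD by the t distribution (0.65 by the normal approximation).

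**Step 2, adjusted.** Two things change.
- The residual variance is multiplied by (1 − R²).
- Estimating p coefficients inflates the variance of the treatment effect by about (N − 3)/(N − p − 3) = 72/(72 − p), and the degrees of freedom fall to 73 − p.

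Example with p = 4 and R² = 0.20: variance ratio = 0.80 × 72/68 = 0.847. SE = 0.231 × √0.847 = 0.213. Noncentrality = 0.5/0.213 = 2.35 on 69 degrees of freedom. Power = 64.0%.

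Power at 0.5 SD, against 57.0% unadjusted:

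| Parameters | R² = 0 | R² = 0.10 | R² = 0.20 | R² = 0.30 |
|---|---|---|---|---|
| 4 | 54.6% | 59.0% | 64.0% | 69.8% |
| 5 | 53.9% | 58.3% | 63.4% | 69.2% |
| 11 | 50.1% | 54.3% | 59.2% | 65.0% |

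**Step 3, break-even.** The variance is unchanged when (1 − R²) × 72/(72 − p) = 1, that is, when R² = p/72. This gives 4/72 = 6%, 5/72 = 7% and 11/72 = 15%.

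**Step 4, how fast parameters add up.** Age (1), ASA as a score (1) and procedure as right, left or total (2) make 4. A separate rectal category makes 5. A longer list adds up quickly: age 1, BMI 1, ASA 1 to 2, procedure 3, preoperative opioid use 1 and institution as fixed indicators 3 to 6 make 10 to 14. With 11 parameters and R² = 0.10, the SE ratio is √(0.90 × 72/61) = 1.03, so the SE rises by 3% and power falls below the unadjusted value.

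**The case against.** The strongest reply is that nothing here is wrong. Unadjusted tests are valid in a randomised comparison. Chance imbalance is part of the sampling error that the unadjusted SE already reflects, so it is not a second harm. This stands: the point concerns efficiency only. A reader might infer from the missing covariates that the planned comparison is biased or invalid, and the documents do not support that.

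The second reply is that the gain is not shown. This also stands in part. The documents give no R², SD or effect size. The covariates most likely to predict pain and opioid use, namely preoperative pain and preoperative opioid use, are not on the collection list. A medical history is taken, but nothing says that opioid use is recorded uniformly. The available covariates may be only modestly prognostic.

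The third reply is that adjustment has a price at this sample size. A reader might infer that it costs nothing, and that power would rise to 61.5%, 66.6% or 72.4% at R² of 0.10, 0.20 or 0.30. Those figures follow from SE × √(1 − R²) with no charge for the estimated coefficients, and they overstate the gain. With a long list, or many surgeon or institution indicators, adjustment can lose power.

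The reply does not remove the case for a short list. With four or five parameters the break-even is 6% to 7%, and the loss if the covariates explain nothing is about 2 to 3 percentage points of power (57.0% to 54.6% or 53.9%).

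**Conclusion.** The point holds as an efficiency improvement. The plan names no adjusted analysis for pain or opioid use, although several baseline variables are collected on everyone and no stratification is described. Under the stated assumptions, a list of four to five parameters raises power by about 1 to 2 percentage points at R² of 0.10, 6 to 7 at 0.20 and 12 to 13 at 0.30. Below an R² of about 6% to 7% it loses slightly.

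The direction is secure only for a short list with some prognostic value. The size rests on assumed R² values and an assumed 0.5 SD effect. The analysed number may also differ from 75: that figure is a minimum, while the Exclusion criteria remove patients converted to open surgery from the analysis. The calculation covers a single comparison and does not model the repeated daily scores.

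**What to change.** In Data analysis/statistics, make the treatment comparison for pain scores and for opioid use in morphine equivalents a linear model, and a mixed model for the daily repeated scores. Specify:

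- arm plus at most about four to five baseline parameters already collected, for example age, ASA score and procedure type, with their coding stated;
- institution as a random effect if more than one enrols, not as fixed indicators, and no set of surgeon indicators;
- preoperative opioid use as one of these covariates only if it is recorded for every patient before randomisation;
- any transformation of opioid dose, fixed in advance and not chosen after looking at the data;
- the outcome and time point to which the model applies, since no primary outcome is named;
- the unadjusted test as a sensitivity analysis.

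The cost is a few sentences of analysis text, plus one chart field if preoperative opioid use is added. No patients or procedures are added. The statistical cost is the small loss of precision shown above if the chosen covariates prove unrelated to outcome.
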